2.3.6 Outcomes

- 1) **Primary outcome:** Our primary outcome will be the difference in mean arterial pressure (MAP) averaged over the 24 hours prior to discharge or the 24 hours prior to antihypertensive therapy initiation (whichever occurs first).
- 2) **Secondary outcomes:** Secondary outcomes will include:
 1. Rates of de novo postpartum preeclampsia – determined at discharge, at 2 and at 6 weeks postpartum
 2. Percentage of recorded blood pressure that are elevated (>140 systolic OR >90 diastolic) – calculated at the time of discharge, at 2 weeks, and at 6 weeks

3. Rates of magnesium sulfate administration – determined at discharge, at 2 and at 6 weeks postpartum
4. Time to discharge
5. Rates of initiation of antihypertensives – determined at discharge, at 2 and at 6 weeks postpartum
6. Rates of severe maternal morbidity (e.g. stroke, seizure, PRES) – determined at 6 weeks postpartum
7. Mean frequency of triage or ED presentation/readmission – determined at 2 and at 6 weeks postpartum
8. Breastfeeding continuation rates – determined at about 2 weeks and at 6 weeks postpartum
9. Neonatal outcomes

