2.2 Specific aims

Our objective is to trial furosemide in women at high risk for developing de novo postpartum hypertension in a randomized control design, with an aim to reduce blood pressure at the time of discharge from the delivery hospitalization and thereby reduce the frequency of postpartum hypertensive episodes requiring therapy and reduce severe morbidity and mortality.

Specific Aim 1. To compare the mean blood pressures over the 24 hours prior to discharge or prior to antihypertensive therapy initiation (whichever occurs first) in women who have been randomized to a 5-day course of PO furosemide 20 mg daily (study drug) to those who have been randomized to a 5-day course of PO placebo daily (placebo). We hypothesize that women taking PO furosemide 20 mg daily will have lower mean blood pressure in the 24 hours

prior to discharge or prior to antihypertensive therapy initiation compared with patients taking placebo.

- **Sub-aim 1: To compare the rates of diagnosis of postpartum hypertension and preeclampsia between those who have been randomized to the study drug and those randomized to placebo from the time of delivery to 6 weeks postpartum.** We hypothesize that women randomized to the study drug will have lower rates of postpartum hypertension and preeclampsia.
- **Sub-aim 2: To compare percentage of elevated blood pressures postpartum between those who have been randomized to the study drug to those randomized to placebo from the time of delivery to 6 weeks postpartum.** We hypothesize that women randomized to the study drug will have fewer hypertensive episodes.
- **Sub-aim 3: To compare the frequency of postpartum hypertension-related triage and emergency department visits between those who have been randomized to the study drug to those randomized to placebo from the time of discharge to 6 weeks postpartum.** We hypothesize that women randomized to the study drug will have fewer triage and emergency department visits for hypertension-related complaints episodes after discharge.
- **Sub-aim 4: To analyze factors associated with response to therapy.** We hypothesize that factors such as degree of lower extremity edema and indication for high risk status will be associated with greater response to therapy.

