2.3.2 Inclusion Criteria

Women who meet the following criteria will be eligible for the study:

- 1) Postpartum women
- 2) No antenatal diagnosis of hypertensive disorder of pregnancy at the time of admission for delivery, defined as existing chronic hypertension diagnosis or documented blood pressure of ≥ 140 systolic OR ≥ 90 diastolic on at least 2 occasions at least 4 hours apart

prior to delivery admission who do not go on to get magnesium for seizure prophylaxis by the time of delivery

- 3) At least 18 years of age
- 4) English or Spanish speakers
- 5) One or more of the following high risk factors and/or two or more moderate risk factors for development of de novo postpartum hypertension:
 - a. High risk
 - i. Pregestational diabetes mellitus
 - ii. Renal disease
 - iii. Autoimmune disease (systemic lupus erythematosus, antiphospholipid syndrome)
 - iv. Multifetal gestation
 - v. Gestational diabetes mellitus, A2 (i.e. medication-dependent)
 - vi. History of preeclampsia in a prior pregnancy (not including the index pregnancy)
 - b. Moderate risk
 - i. Primiparity
 - ii. Obesity (BMI $\geq 35 \text{ kg/m}^2$)
 - iii. Age ≥ 35 years
 - iv. Black or African-American race
 - v. Family history of preeclampsia

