2.3.8 Definitions

Chronic hypertension will be defined according to ACOG guidelines as blood pressure measurement of EITHER ≥ 140 mm Hg OR diastolic ≥ 90 mm Hg on at least 2 occasions, at least 4 hours apart, prior to 20 weeks gestation.²

Hypertensive disorders of pregnancy will be defined according to ACOG guidelines.² The minimum criteria for a diagnosis of HDP are as follows:

- Blood pressure measurement of EITHER systolic ≥ 140 mm Hg OR diastolic ≥ 90 mm Hg on at least 2 occasions, at least 4 hours apart, between 20 weeks gestation and delivery
- Blood pressure measurement of EITHER systolic ≥ 160 mm Hg OR diastolic ≥ 110 mm Hg on at least 2 occasions qualifies as severe features

Diagnosis of hypertensive disorder of pregnancy will be determined at the time of admission for delivery.

The following investigations are routinely undertaken in the clinical setting once HDP is identified in order to further categorize HDP into more specific diagnoses. These results will be reviewed for each patient to ensure the correct diagnosis has been assigned to the patient. Blood pressure findings as above with none of the findings listed in the table below satisfies a diagnosis of gestational hypertension.

Type of test	Cutoffs	Diagnosis
--------------	---------	-----------

Urine	
 -24-hour protein concentration > 300 mg OR -Protein/Creatinine ratio > 0.3 	Preeclampsia
Serum	
 -Platelets $<100,000/\text{microliter}$ OR -Creatinine $>1.1 \text{ mg/dL}$, or doubling from baseline OR -LFTs $>$ twice the upper limit of normal concentration or twice baseline 	Preeclampsia with severe features
Signs/symptoms: any of the following, if not accounted for by another diagnosis	
 -New-onset, refractory cerebral or visual disturbances -Severe persistent right upper quadrant or epigastric pain unresponsive to medication -Pulmonary edema -Blood pressure ≥ 160 systolic OR ≥ 110 diastolic 	Preeclampsia with severe features
Serum	
 -Platelets $<100,000/\text{microliter}$ AND -Evidence of hemolysis AND -LFTs $>$ twice the upper limit of normal concentration or twice baseline 	Hemolysis, elevated liver enzymes and low platelet count (HELLP) syndrome
Signs/symptoms	New-onset, grand mal seizure, with no history of seizure disorder and not accounted for by any other diagnosis	Eclampsia

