De novo postpartum hypertensive disorders of pregnancy will be defined according to the aforementioned criteria and definitions, except for their timing of occurrence after delivery, and in the absence of any antenatal diagnosis of a hypertensive disorder of pregnancy.

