2.4 Statistical Analyses

2.4.1 Sample size and statistical power

A case-control study of women who were normotensive at delivery but who were later hospitalized with a diagnosis of severe preeclampsia compared to women who remained normotensive in the postpartum period and women who were diagnosed with preeclampsia in the antenatal period determined that differences in mean arterial blood pressure could be detected following delivery. This retrospective review determined that women who developed de novo postpartum preeclampsia had a greater increase in MAP after delivery than normotensive women (5.0 ± 6.4 mm Hg vs 0.2 ± 6.0 mm Hg, $p < 0.004$).¹³ Though data is scarce on whether a change in MAP can be detected in women with a broader diagnosis of de novo postpartum hypertension, using this reference data to assign an effect size of 5 mm Hg with standard deviation of 6.4 mm Hg and a baseline MAP of 83 mm Hg will provide a conservative estimate of a clinically meaningful change. For a power of 90%, a significance level 5%, and anticipated post-randomization losses of 10%, 41 patients will be needed for each group, or 82 patients total.

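### Secondary outcome 2 counts a reading as elevated only above 140/90, whereas every 140/90 definition of hypertension in the protocol starts at 140/90

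*Combined protocol and SAP*

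**What the plan says.** Section 2.3.6 lists secondary outcome 2 as "Percentage of recorded blood pressure that are elevated (>140 systolic OR >90 diastolic", calculated at discharge, 2 weeks and 6 weeks. Both inequalities are strict.

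The other 140/90 limits in the protocol are inclusive:

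- Section 2.3.2, inclusion criterion 2: "documented blood pressure of ≥ 140 systolic OR ≥ 90 diastolic on at least 2 occasions at least 4 hours apart".
- Section 2.3.8, chronic hypertension: "blood pressure measurement of EITHER ≥ 140 mm Hg OR diastolic ≥ 90 mm Hg on at least 2 occasions".
- Section 2.3.8, hypertensive disorder of pregnancy: "Blood pressure measurement of EITHER systolic ≥ 140 mm Hg OR diastolic ≥ 90 mm Hg on at least 2 occasions".

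Section 2.3.8 then applies these limits after delivery: "De novo postpartum hypertensive disorders of pregnancy will be defined according to the aforementioned criteria and definitions", changing only the timing and requiring that there was no antenatal diagnosis. Its severe-range limits (≥160, ≥110) are inclusive too.

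In section 2.2, Sub-aim 2 of Specific Aim 1 compares the percentage of elevated pressures and attaches this hypothesis: "We hypothesize that women randomized to the study drug will have fewer hypertensive episodes". Sections 2.3.1 and 2.3.7 also call for counts or incidence of elevated readings, without giving a cutoff.

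**The concern.** The outcome that is meant to measure hypertensive episodes draws its line in a different place from the protocol's own definition of hypertension. A reading with one component exactly on its limit, and the other not above its limit, counts towards a diagnosis but not towards the percentage elevated. The protocol does not explain the difference.

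At stake is the level of one secondary outcome and its agreement with the diagnoses reported beside it. The same woman could be a diagnosed case of de novo postpartum hypertension with no elevated readings. Since sections 2.3.1 and 2.3.7 use the term without a cutoff, someone programming those counts would have to choose between the two rules.

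**Working it through.** **Which readings are affected.** The strict rule counts a reading if systolic >140 or diastolic >90. The inclusive rule counts it if systolic ≥140 or diastolic ≥90.

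| Reading | Inclusive (2.3.2, 2.3.8) | Strict (2.3.6) |
|---|---|---|
| 140/85 | meets limit | not elevated |
| 130/90 | meets limit | not elevated |
| 140/90 | meets limit | not elevated |
| 140/95 | meets limit | elevated (diastolic above 90) |
| 141/85 | meets limit | elevated |

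Only the first three rows differ. Two readings of 140/85 at least 4 hours apart satisfy the diagnostic pressure limit in section 2.3.8 and contribute 0 of 2 to secondary outcome 2.

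**How many readings that might be.** The plan states no figure for this outcome, so there is nothing to reproduce. It gives no systolic or diastolic distribution either, so one has to be assumed. The only anchors are in section 2.4.1: "a baseline MAP of 83 mm Hg", and a mean MAP rise of 5.0 mm Hg in women who went on to de novo postpartum preeclampsia.

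Assumptions: whole-number readings, bivariate normal, SD 12 systolic and 9 diastolic, correlation 0.6. With MAP = (systolic + 2 × diastolic)/3, one split that gives 83 is 113/68, since (113 + 136)/3 = 83. Adding 5 to each component gives 118/73, with MAP (118 + 146)/3 = 88.

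With F the bivariate normal distribution function and half-unit bounds for whole numbers:

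- share at or above the limit = 1 − F(139.5, 89.5)
- share above the limit = 1 − F(140.5, 90.5)

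| Mean reading | MAP | ≥140/90 | >140/90 | Loss, points | Loss, % of qualifying readings |
|---|---|---|---|---|---|
| 113/68 | 83.0 | 2.00% | 1.57% | 0.43 | 21% |
| 118/73 | 88.0 | 6.03% | 4.91% | 1.12 | 19% |
| 126/80 | 95.3 | 21.60% | 18.67% | 2.93 | 14% |
| 135/85 | 101.7 | 46.55% | 42.51% | 4.03 | 9% |

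Sensitivity over SD 10/7, 12/9 and 14/11 and correlation 0.4, 0.6 and 0.8: the loss is 0.12 to 0.84 points (16% to 28% of qualifying readings) at 113/68, and 3.3 to 5.1 points (7% to 12%) at 135/85.

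**End-digit rounding.** The figures above assume no preference for round numbers. If 30% of values are rounded to the nearest 10 (also an assumption), simulation at SD 12/9 and correlation 0.6 gives a loss of 2.67 points at a mean of 115/70 and 13.01 points at 130/82. Without rounding the same means give 0.64 and 3.53.

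**Effect on the comparison between arms.** Take 118/73 in one arm and 113/68 in the other, a shift equal to the 5 mm Hg effect size in section 2.4.1.

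- Inclusive: 6.03% against 2.00%, a ratio of 3.0 and a difference of 4.0 points.
- Strict: 4.91% against 1.57%, a ratio of 3.1 and a difference of 3.3 points.

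**The case against.** The strongest reply is that nothing that decides the trial depends on this. The outcome can be computed as written and the rule is the same in both arms. Diagnoses are made under section 2.3.8 with the inclusive limit, and the between-arm ratio hardly moves (3.0 against 3.1). All of that stands, and it is why the point is minor.

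A second reply is that sections 2.3.2 and 2.3.8 define diagnoses, which need two occasions at least 4 hours apart, while outcome 2 classifies single readings. The purposes do differ, and taking the diagnostic limit as the reference for Sub-aim 2 is an inference, because hypertensive episodes are not defined. But that difference accounts for the repeat requirement. It does not account for a different boundary on each reading.

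A third reply concerns the size. A cohort mean of 135/85 has a MAP of 101.7, well above the 83 to 88 that section 2.4.1 supports, so the 4-point figure is an upper illustration. The 21% is a share of a 2% base. The rounding results show that the smooth-normal ranges do not bound the effect. These cautions are fair: the percentages illustrate a definitional mismatch and do not estimate what this trial will see.

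**Conclusion.** The concern holds, as a minor inconsistency. Secondary outcome 2 as written uses a different boundary from every other 140/90 limit in the protocol, without explanation, and leaves out readings that the protocol's own limit treats as hypertensive.

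Near the MAP values the documents support (83 to 88), the outcome would be understated by about 0.4 to 1.1 percentage points, given normal whole-number readings, SD 12/9 and correlation 0.6. The loss would be larger with higher pressures or with rounding to round numbers. The mismatch itself rests on the text alone and needs none of these assumptions. There is no between-arm bias, no lost diagnosis, and no effect on the primary MAP outcome or on the 41 patients per group.

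**What to change.** In section 2.3.6, change secondary outcome 2 to systolic ≥140 or diastolic ≥90, matching sections 2.3.2 and 2.3.8. If the strict sign is intended, say why. Either way, state that the same cutoff governs elevated readings in Sub-aim 2 (section 2.2) and in sections 2.3.1 and 2.3.7, and settle this before the data are analysed.

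The cost is two symbols and a cross-reference. No new data are needed and the sample size does not change.

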Specific Aim 2. To compare rates of initiation of hypertensive therapies in women randomized to the study drug compared to those randomized to placebo. We hypothesize that women randomized to the study drug will be less likely to be initiated on hypertensive therapies between delivery and 6 weeks postpartum.

Specific Aim 3. To compare rates of severe maternal morbidity in women randomized to the study drug compared to those randomized to placebo from the time of discharge to 6 weeks postpartum. We hypothesize that women randomized to the study drug will have lower rates of severe maternal morbidity between delivery and 6 weeks postpartum compared to those randomized to placebo.

- **Sub-aim 1: To compare hypertensive-related unscheduled presentations between those who have been randomized to the study drug and those randomized to placebo.** We hypothesize that women randomized to the study drug will have fewer triage and emergency department visits for hypertension-related complaints episodes after discharge.
- **Sub-aim 2: To assess adverse effects of therapy in the study group and the control group.** We hypothesize that there will be no difference in adverse effects, such as discontinuation of breastfeeding, hypotension, and electrolyte abnormalities in women randomized to the study drug compared to those randomized to placebo.
- **Sub-aim 3: To analyze factors associated with incidence of severe maternal morbidity in the study group and the control group.** We hypothesize that factors such as racial and ethnic identity and age will be associated with increased incidence of severe maternal morbidity.

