Patient written informed consent and HIPAA authorization to participate in the study will be collected on an iPad or laptop. In-person electronic signature will be captured on the electronic informed consent form. Study personnel obtaining consent will be physically present at time of signature. A paper copy of the signed informed consent form will be given to the patient. A copy of the signed consent form will also be placed in the patient's inpatient paper chart. The time of consent will be documented on the consent form and in the medical record.

Consent forms will be available in both English and Spanish to accommodate our expected population. A witness will be required for our non-English speaking patients.

At the time of the consent, the Informed Consent Process will begin with a concise and focused presentation of the key information about the research study. The collaborating investigators will explain the study, and potential subjects will have an opportunity to discuss the information provided. The collaborating investigators will answer any questions. The Informed Consent Process as a whole presents information in sufficient detail relating to the research study. Consent will be obtained to measure blood pressures postpartum. Consent will be obtained to review medical records to abstract pertinent sociodemographic and clinical information and to call patients to obtain the aforementioned information if not able to be abstracted from the medical record. Consent will be obtained to administer electronic surveys and collect home blood pressure measurements at two postpartum study visits. Patients still meeting inclusion criteria will be randomized at within eight hours of delivery on the postpartum service.

Enrollment

After obtaining written informed consent, participants will be randomized to either the study drug, as defined above, or placebo. Randomization will occur through the Columbia Research Pharmacy in REDCap. The medication intervention will be dispensed to the patient's postpartum unit and administered by the nursing staff once daily beginning within eight hours of delivery. The patient, the patient's nurse, and the patient's inpatient obstetric provider will not be informed

of the patient's randomization group, to avoid potential biases stemming from differences in inpatient care. Participants will be enrolled in the study from the time of randomization until 6 weeks postpartum.

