2. **Adherence.** For both groups, proportion of medication course completed will be recorded
3. **Time to initiation of medications.** For both groups, time to initiation of anti-hypertensive medications will be tracked
4. **Final plan at 6 weeks.** For both groups, continuing medication regimens at 6 weeks will be collected.
5. **Hospital readmissions.** Hospital readmission for any indication will be collected for both groups
6. **Triage/ED visits.** Presentation to the obstetric triage unit or the emergency department for any indication will be collected for both groups
7. **Maternal morbidity and mortality.** Incidences of eclampsia, stroke, PRES, maternal death will be collected for both groups
8. **Breastfeeding continuation.** Rates of breastfeeding continuation will be collected for both groups
9. **Adverse effects.** Incidences of hypotension, electrolyte abnormalities, and development of renal insufficiency will be collected for both groups.

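### Secondary outcome 7 counts triage/ED visits and readmissions with no cause restriction, while the two sub-aims it would serve ask about hypertension-related visits

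*Combined protocol and SAP*

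**What the plan says.** Two sub-aims in section 2.2 concern use of care because of high blood pressure.

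- Aim 1 Sub-aim 3: "To compare the frequency of postpartum hypertension-related triage and emergency department visits". The arms are compared over the period from discharge to 6 weeks.
- Aim 3 Sub-aim 1: "To compare hypertensive-related unscheduled presentations between those who have been randomized to the study drug and those randomized to placebo". Its hypothesis is "fewer triage and emergency department visits for hypertension-related complaints episodes after discharge" in the furosemide arm.

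Section 2.3.6 lists secondary outcome 7 as "Mean frequency of triage or ED presentation/readmission", assessed at 2 and 6 weeks. It says nothing about the cause of the visit.

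Section 2.3.7, in the list of data collected throughout the study, has two separate items. Item 5 reads "Hospital readmission for any indication will be collected for both groups". Item 6 reads "Presentation to the obstetric triage unit or the emergency department for any indication will be collected for both groups". Neither asks for the reason.

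On access to source data, section 2.3.4 says: "Consent will be obtained to review medical records to abstract pertinent sociodemographic and clinical information". It also allows calls to patients for information that the record does not supply.

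No section defines a hypertension-related visit, lists a visit-reason field, or says who would classify a visit. Section 2.4.2 gives no rule specific to this outcome.

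**The concern.** The objective and the outcome differ on cause. A team that follows sections 2.3.6 and 2.3.7 to the letter would count a visit for a wound check or bleeding the same as a visit for severe-range blood pressure, and would then report the total against sub-aims about hypertension.

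Four things are at stake.

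- **Dilution.** Visits that the drug does not affect add equally to both arms. They shrink the relative difference and add variance.
- **Opposing effects.** Section 2.10.1 lists dehydration, hypotension, weakness and arrhythmia among the risks of furosemide. Visits for these would enter the same count and could offset a real benefit on hypertension.
- **Episode counting.** With presentation and readmission in one item, a triage visit that ends in admission could count once or twice. No rule is given.
- **Late classification.** If the hypertension-related subset is defined only at analysis, the choice is discretionary. Section 2.3.4 keeps the allocation from the woman, her nurse and her inpatient obstetric provider. It does not mention chart abstractors or analysts.

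**Working it through.** **1. The plan's own figure.** The plan states no rate, effect or sample size for this outcome. Its only sample size, 82 in section 2.4.1, is for MAP. A two-sided two-sample t-test with difference 5, SD 6.4, alpha 0.05 and power 90% needs 36 per group. Then 36/(1 − 0.10) = 40 per group, or 80 in total, within 2 patients of 82. The figure is reproduced closely, but it neither supports nor refutes this point.

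**2. The texts side by side.**

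| Place | Event | Cause |
|---|---|---|
| 2.2, Aim 1 Sub-aim 3 | triage and ED visits | hypertension-related |
| 2.2, Aim 3 Sub-aim 1 | unscheduled presentations (hypothesis: triage and ED visits) | hypertension-related |
| 2.3.6, outcome 7 | triage or ED presentation and readmission, one item | not stated |
| 2.3.7, items 5 and 6 | readmissions; triage/ED visits, two items | any |

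No other section closes the gap. The surveys in section 2.3.1 cover symptoms and breastfeeding, not reasons for visits. In section 2.10.4 the rule to record all adverse events covers consent to the end of study drug intake, up to 5 days after delivery, while the sub-aims run to 6 weeks. The 2-week and 6-week follow-up there also looks for adverse events, but nothing ties it to classifying visits.

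**3. Dilution in a count (assumed inputs).** Let T be the mean number of visits per woman on placebo and f the hypertension-related share. Assume that the drug halves that share and leaves the rest unchanged.

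- Absolute difference, the same for both counts: d = 0.5fT.
- Relative fall in the all-cause count: d/T = 0.5f.
- Variance of the between-arm difference for Poisson counts is proportional to 2T − 0.5fT for all-cause visits and to fT + 0.5fT = 1.5fT for hypertension-related visits. The ratio is (2 − 0.5f)/(1.5f).

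| f | Fall in all-cause count | Variance ratio |
|---|---|---|
| 0.2 | 10% | 1.90/0.30 = 6.33 |
| 0.3 | 15% | 1.85/0.45 = 4.11 |
| 0.5 | 25% | 1.75/0.75 = 2.33 |
| 0.8 | 40% | 1.60/1.20 = 1.33 |

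**4. A second model: at least one visit per woman (assumed inputs).** Take 37 per arm (41 × 0.9 = 36.9). Let p be the risk of a hypertension-related visit, halved by the drug, and u an independent risk of an unrelated visit, equal in both arms. The all-cause risk is 1 − (1 − p)(1 − u). With p = 20% on placebo and 10% on furosemide:

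| u | Placebo | Furosemide | Risk ratio | Power | n per arm for 80% power |
|---|---|---|---|---|---|
| 0 (cause-specific) | 20% | 10% | 0.50 | 22% | 199 |
| 10% | 28% | 19% | 0.68 | 15% | 348 |
| 30% | 44% | 37% | 0.84 | 9% | 771 |

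Over placebo risks of 10% to 30%, the cause-specific risk ratio of 0.50 moves to 0.64–0.76 with u = 10% and to 0.79–0.90 with u = 30%. Power for the cause-specific outcome is 12% to 34%. It falls to 7%–24% with u = 10% and to 5%–14% with u = 30%.

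**The case against.** The strongest reply is that outcome 7 is a short label whose qualifier stands in section 2.2, and that capturing all visits is the right way to collect the data, because the hypertension-related ones are a subset. Section 2.3.4 provides for chart review and calls to patients. Section 2.10.4 has the team follow the postpartum course at about 2 and 6 weeks and be told of readmissions before a follow-up visit. The data-collection form is not among the documents. A reader might infer that no reason will be recorded, so that the sub-aims cannot be answered. The documents do not support that: they leave the reason unspecified, and it is probably recoverable.

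A reader might also infer that unrelated visits will swamp any effect. No visit rate is given, so this is a scenario and not a finding. The women are selected for high risk and measure their blood pressure at home, so the hypertension-related share could be large; at 80% the variance ratio is only 1.33. Nor can it be assumed that furosemide affects hypertension-related visits alone, given section 2.10.1. All-cause use is a legitimate measure of net effect and needs no judgement about cause.

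Two further limits are fair. Pooling with readmission occurs only in outcome 7, since section 2.3.7 lists the items apart. The phrase unscheduled presentations in Aim 3 Sub-aim 1 can reasonably include an unplanned readmission.

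All of this stands, and it narrows the point. The label reading does not remove it: the outcome list and the data items both omit the qualifier, and nothing requires, defines or assigns the classification.

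**Conclusion.** The concern holds as a misalignment between objective and outcome. Outcome 7, analysed as written, estimates all-cause use of care, whereas Aim 1 Sub-aim 3 and Aim 3 Sub-aim 1 ask about hypertension-related visits. That rests on the text alone and is firm.

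The size of the consequence is not known. The 10% to 25% fall in the all-cause count assumes a halving of hypertension-related visits, a share of 20% to 50%, and no drug effect on other visits. A larger share makes the loss smaller, and drug-related visits could move the count either way.

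Realignment makes the estimate match the question but does not make the comparison well powered. Under the assumed risks even the cause-specific outcome has only about 12% to 34% power with 37 per arm, so a null result would say little under either definition. This is a secondary outcome and the primary MAP analysis is unaffected. It should be corrected, but it does not threaten the trial.

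**What to change.** - In section 2.3.6, restate outcome 7 as the number of hypertension-related triage/ED presentations after discharge, keeping both the 2-week and the 6-week assessments.
- Define hypertension-related in advance, for example in section 2.3.8, and state how a presentation that leads to admission is counted.
- In section 2.3.7, add a reason field (hypertension-related, yes or no) to items 5 and 6, abstracted from the chart by someone who does not know the arm.
- Report hypertension-related readmissions on a separate line.
- Keep the any-indication counts of visits and readmissions as supportive safety data, which also covers possible drug-related visits.

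The cost is one reworded outcome, one definition and one added field for each of the two data items, taken from records that participants already consent to have reviewed. The downside is some judgement in assigning reasons, which blinded classification against a fixed definition keeps from favouring either arm.
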